1.2 Study Design

In this Phase 2, multicenter, randomized, open-label study, the PK, safety, and efficacy of bimekizumab in male and female adolescents (from 12 to <18 years of age) with moderate to severe plaque PSO will be assessed.

The PK, safety, and efficacy of bimekizumab will be evaluated by treating at least 20 participants in each of 2 dose groups (for a total of at least 40 participants evaluable for PK). Both doses are expected to be efficacious based on exposure-response (E-R) predictions. Dose A (320mg every 4 weeks [Q4W] in participants ≥ 65 kg and 160mg Q4W in participants <65kg) is predicted to provide the same systemic bimekizumab exposure as the 320mg Q4W adult dose, and Dose B (64mg Q4W in participants ≥ 65 kg and 32mg Q4W in participants <65kg) is aimed at providing a lower systemic bimekizumab exposure. Weight-based dosing during the Initial Treatment Period will be based on the participant's weight at Baseline.

This study will consist of the following periods:

- Screening Period: up to 5 weeks
- Initial Treatment Period: 20 weeks (5 doses of bimekizumab; administered at Baseline, Week 4, 8, 12, and 16 followed by 4 weeks of observation)
- Open-label Extension (OLE) Period: 104 weeks (bimekizumab administration starts at Week 20 if participant is eligible)
- Safety Follow-up (SFU) Period: 20 weeks after the final dose of bimekizumab

After the Screening Period of up to 5 weeks, eligible participants will be randomized to 1 of the 2 dose groups. The randomization will be stratified by weight category. During the Initial Treatment Period, participants will receive 5 doses of open-label bimekizumab (at Weeks 0 [Baseline], 4, 8, 12, and 16). Participants who complete the Initial Treatment Period, tolerate the treatment, and achieve an IGA response ≤ 2 at Week 20 may continue bimekizumab treatment at the same dose level in the OLE Period.

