5.2 Study Participant Dispositions

The number and percentage of participants who are screened, enrolled, and randomized will be summarized for each clinical site and overall. Number and percentages of screen failures will also be summarized in the ES, and summaries of reasons for screen failures will be produced. The participants who discontinued treatment, discontinued study, or completed the study, as well as the discontinuation reasons, will be summarized for study periods by dose group in the RS. The overall number and percentages will also be summarized.

In addition, the number and percentages of participants in each of the analysis sets (ES, RS, SS, PK-PPS, and OLS) will be summarized by treatment arm and overall.

For purposes of summarizing disposition, study participants will be considered to have completed a study period if they complete the last scheduled study visit during that study period, not including SFU visits. A participant will be considered to have completed the study as follows:

- Completion of Initial Treatment Period is defined as completing the Week 20 Visit and the completion date is the Week 20 Visit date.
- Completion of OLE Period: for participants who entered the OLE period, completion is defined as completing the Week 124 Visit, and the completion date is the Week 124 visit.
- Completion of Study: For all participants, completion of study is considered as completion of OLE Period. Participants who do not tolerate the IMP or who have an IGA response ≥ 3 (on a scale from 0 to 4) at Week 20 will be considered as withdrawn from the study due to lack of efficacy. Participants who are eligible for but elect not to enter the OLE period at Week 20 will be considered as withdrawn from the study due to consent withdrawn.

In parallel, the end date of the study for a participant will be defined considering SFU Visit: the later date of the last visit including SFU or the date of last known dose of study drug.

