5.4.1.2 Main analytical approach

5.4.1.2.1 PASI90 (Week 16) response

The estimand for the secondary efficacy endpoint PASI90 response at Week 16 is defined as follows:

- **Participant-level outcome:** PASI90 response at Week 16.
- **Treatment:** Bimekizumab high dose (Dose A) and low dose (Dose B).
- **Population:** Study participants enrolled according to the protocol-specified inclusion/exclusion criteria and randomized to IMP.
- **Intercurrent event handling:** An intercurrent event is defined as discontinuation of IMP prior to Week 16. A composite strategy will be implemented in which a positive clinical outcome is defined as achieving PASI90 response at Week 16 and not discontinuing IMP through Week 16.
- **Population-level summary:** Percentage of participants achieving PASI90 response at Week 16 in each dose group.

The number and percentages of PASI90 responders at Week 16 will be reported for each dose group with 95% CIs. Missing data not preceded by an intercurrent event will be imputed as nonresponse for this and other binary secondary efficacy variables. An OC method will also be implemented to assess the impact of the main method of handling missing data.

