5.6.2.2 AE summaries

The following AE summaries for participant incidence and event number will be provided by weight-categorized dose group for the Initial Treatment Period, OLE Period, and the combined periods. Selected summaries as noted will report exposure adjusted rates. An overall summary of the AEs will also be provided. AE tables will summarize Dose A (320mg, 160mg, Total), Dose B (all) and All Participants on one page; the subsequent page will contain Dose B (64mg, 32mg, Total), Dose A (all) and All Participants.

- Summary by system organ class (SOC), HLT, and preferred term (PT):
 - Any TEAE (with exposure-adjusted rates)
 - Serious TEAE (with exposure-adjusted rates)
 - TEAEs leading to withdrawal from the study (with exposure-adjusted rates)
 - TEAE leading to discontinuation of investigational medicinal product (IMP) (with exposure-adjusted rates)
 - TEAE leading to death
 - Related TEAE
 - Related serious TEAE
 - TEAE for safety topics of interest and safety topics closely monitored (with exposure-adjusted rates)
- Summary by relationship, SOC, HLT, and PT
 - Any TEAE
 - TEAE leading to death (for EudraCT reporting purposes)
- Summary by maximum relationship, SOC, HLT, and PT
 - Any TEAE
- Summary by severity, SOC, HLT, and PT
 - Any TEAE
- Summary by maximum severity, SOC, HLT, and PT
 - Any TEAE

Ordered and subset of AE summaries will be reported in a separate table to facilitate review when needed. Examples include:

- Serious TEAE by SOC and PT
- Nonserious TEAE by SOC and PT above reporting threshold of 5%

- Any TEAE by decreasing frequency of PT

The following summary will be provided for antibody data (Section 5.7.1.4.1.6 and Section 5.7.1.4.2.1):

- Incidence of TEAEs per 100 participant years by SOC, HLT, and PT and by time of onset relative to ADAb status. Note: Only presented for combined Initial Treatment Period and OLE Period.
- Incidence of TEAEs per 100 participant years by SOC, HLT, and PT and by time of onset relative to NAB status. Note: Only presented for combined Initial Treatment Period and OLE Period.

The following AEs will be listed separately:

- Any TEAE with onset at day 1
- Any TEAE related to TB including latent TB and IGRA tests

The following summaries will be produced for the Plain Language Summaries:

- Incidence of Drug-related TEAEs – Overview
- Incidence of Drug-related TEAEs by Preferred Term
- Incidence of Serious Drug-related TEAEs by Preferred Term

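### SAP 5.2 records participants who cannot tolerate the IMP as study withdrawals for lack of efficacy, so the dose-group disposition table can give the wrong reason

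*SAP*

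**What the plan says.** SAP 5.2 (Study Participant Dispositions) sets completion as follows: "For all participants, completion of study is considered as completion of OLE Period". Anyone who does not enter the open-label extension (OLE) therefore counts as a study withdrawal and needs a reason.

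For the Week 20 decision the section supplies two reasons.

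- **Lack of efficacy.** The rule opens with "Participants who do not tolerate the IMP or who have an IGA response" of 3 or more, and says that these participants "at Week 20 will be considered as withdrawn from the study due to lack of efficacy".
- **Consent withdrawn.** "Participants who are eligible for but elect not to enter the OLE period at Week 20 will be considered as withdrawn" for that reason.

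The same section says what is tabulated: "The participants who discontinued treatment, discontinued study, or completed the study, as well as the discontinuation reasons", by study period and dose group in the Randomized Set.

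SAP 1.2 and Protocol 4.1 state the conditions for entering the OLE. "Participants who complete the Initial Treatment Period, tolerate the treatment, and achieve an IGA response" of 2 or less at Week 20 may continue. Tolerating treatment and having a low enough IGA are separate requirements.

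**The concern.** Not tolerating a drug and not responding to it are different outcomes, and a disposition table by dose group exists partly to tell them apart. The SAP rule merges them under the efficacy label. A participant with clear or almost clear skin who cannot continue because of intolerance would be reported as an efficacy failure.

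Two inconsistencies can follow in the study report. The same person can count as a PASI90 and IGA 0/1 responder at Week 16 and as a lack-of-efficacy withdrawal 4 weeks later. And if the intolerance is recorded as an adverse event leading to withdrawal, that person appears as an adverse-event withdrawal in the safety tables and as an efficacy withdrawal in disposition.

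**Working it through.** The plan states no figure to reproduce. The check is a comparison of texts, followed by a scale calculation.

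**1. How the documents treat the two conditions**

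| Place | Intolerance | IGA of 3 or more at Week 20 |
|---|---|---|
| Protocol 4.1 and SAP 1.2, OLE entry | one condition | a separate condition |
| Protocol 4.1 and SAP 1.2, Week 20 withdrawal | withdrawn, no reason named | withdrawn, no reason named |
| Protocol 7.2, withdrawal criteria | no. 10, discussed with the Medical Monitor | no. 6, mandatory |
| SAP 5.2, disposition | lack of efficacy | lack of efficacy |

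The efficacy label for intolerance appears only in SAP 5.2. It is current text, and nothing else in the SAP gives these participants another reason.

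**2. Applying the rule to each Week 20 case**

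| IGA | Tolerates IMP | Outcome | Reason under SAP 5.2 | Suitable? |
|---|---|---|---|---|
| 3 or more | yes | withdrawn | lack of efficacy | yes |
| 3 or more | no | withdrawn | lack of efficacy | depends on the primary reason |
| 2 or less | no | withdrawn | lack of efficacy | **no** |
| 2 or less | yes | eligible, declines OLE | consent withdrawn | yes, given the SAP's completion definition |
| 2 or less | yes | enters OLE | none needed | – |

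The third row is the error. That participant is not eligible for the OLE, so the consent-withdrawn reason cannot apply and only lack of efficacy is left.

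**3. Compatibility with Week 16 response**

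SAP 5.4.1.2.1 says: "An intercurrent event is defined as discontinuation of IMP prior to Week 16". A participant who stays on IMP through Week 16 and is found intolerant afterwards has no intercurrent event for the Week 16 endpoints and can be a responder. The gap to the Week 20 decision is 20 − 16 = 4 weeks.

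**4. Compatibility with the safety tables**

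SAP 5.6.2.2 plans "TEAEs leading to withdrawal from the study (with exposure-adjusted rates") and a similar table for discontinuation of IMP. If the intolerance is entered as a TEAE leading to withdrawal, the safety and disposition tables give different reasons for one person.

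**5. Scale**

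SAP 1.2 plans at least 20 participants in each of 2 dose groups, at least 40 in total. Shift in the lack-of-efficacy row per affected participant = 1/n:

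- one arm, n = 20: 1/20 = 5.0 percentage points
- overall, n = 40: 1/40 = 2.5 percentage points
- no affected participants: 0 points

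Larger arms give a smaller shift per participant. The documents give no expected number of cases.

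**The case against.** The strongest reply is that little depends on this row. All analyses are descriptive. The estimands do not use the withdrawal reason. Intolerance still shows in the treatment-discontinuation reasons and in the tables of TEAEs leading to IMP discontinuation or study withdrawal. Nothing in the documents uses disposition reasons to choose the PS0021 dose. All of this stands, and it limits the finding to one row of one table.

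The affected group is also narrow. The clear error needs someone who reaches Week 20 with IGA of 2 or less and is kept out of the OLE for intolerance alone. Participants who stop IMP earlier may keep their eCRF reason. That is only partly reassuring: Protocol 7.1 encourages people who have stopped IMP to attend visits through Week 20, and SAP 5.2 counts attendance at that visit as completing the Initial Treatment Period, so the literal rule could reach them too.

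The Week 16 pairing is not a contradiction in itself, since a Week 16 responder may relapse to IGA of 3 or more by Week 20 and properly be an efficacy withdrawal. That is correct. The conflict arises only when IGA is still 2 or less at Week 20.

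Finally, the intolerance wording may simply have been carried over, because the Protocol 1.1 synopsis names only IGA of 3 or more as the Week 20 withdrawal rule. That may explain its origin, but it does not change what would be programmed. Deleting the phrase alone would leave intolerant participants with no stated reason, because SAP 5.2 would still count them as non-completers.

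**Conclusion.** The concern holds. As written, SAP 5.2 assigns the wrong study-withdrawal reason to a participant who has IGA of 2 or less at Week 20 and does not enter the OLE because of intolerance. It should be corrected, although its reach is small: 5 percentage points per affected participant in a 20-participant arm, 2.5 points among 40 overall, and nothing if no such participant exists. These figures assume arms at the planned minimum.

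The conclusion rests on reading the sentence literally, as a programmer would. PK, efficacy, adverse-event tables, the Open-label Set and dose selection are unaffected.

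**What to change.** Replace the sentence in SAP 5.2 with:

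> Participants with IGA ≥3 at Week 20 will be considered withdrawn from the study due to lack of efficacy. Participants who do not enter the OLE because they do not tolerate the IMP will be considered withdrawn for the primary reason recorded on the eCRF (eg, adverse event), not lack of efficacy. If both apply, the eCRF primary reason is used.

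The last sentence is an exception to the first. Everyone who does not enter the OLE for either reason still has a withdrawn status.

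The cost is one SAP sentence and the matching line of disposition programming. Protocol 7.3, in the context of loss to follow-up, requires the eCRF to hold a primary reason for withdrawal. The eCRF reason categories are not in the documents, so the team should confirm that a suitable one exists. The SAP version history gives database lock as part of the rationale for version 3.0. If the database is already locked, a documented SAP correction or a note in the study report is enough.

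This change keeps the SAP's definition of study completion. Protocol 4.4 differs: it counts participants who do not enter the OLE as completers once they finish the Initial Treatment Period and the SFU Visit. That is a separate matter which this change does not resolve.

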5.2.1 COVID-19 impact analysis

The World Health Organization (WHO) declared the novel COVID-19 outbreak a global pandemic on 11 Mar 2020. For the purposes of summarizing disposition with respect to COVID, post-COVID refers to an event or record reported after the date when WHO declares the global pandemic has ended. If the WHO has not declared an official end date, an alternative end date may be used at the discretion of study team. If no suitable end date exists, the global pandemic is considered ongoing.

To assess the impact of the COVID-19 pandemic on the study, the following summaries will be presented:

- A summary of study visits impacted by the COVID-19 pandemic, and associated listing

5.3 Primary Endpoint Analysis

The primary analysis for this study is the PK analysis, outlined in Section 5.7.1.1.

5.4 Secondary Endpoints Analysis

Secondary variables include safety variables, efficacy variables, QOL variables, and immunogenicity variables. This section will outline the analysis for the secondary efficacy and QOL variables. The analysis for safety and immunogenicity variables will be presented in Section 5.6 and Section 5.7.1.4.

5.4.1 Secondary endpoints

5.4.1.1 Definition of endpoints

5.4.1.1.1 PASI response

The PASI is the most used and validated assessment for grading the severity of PSO in clinical studies (Feldman, 2004) and will be completed by the Investigator.

The percent body surface area of PSO involvement (BSA%) is estimated across the 4 body areas, head, upper limbs, trunk, and lower limbs. The BSA% is then converted into a degree score on a scale of 0 to 6 (0=none; 1=1% to <10% affected, 2=10% to <30% affected, 3=30% to <50% affected, 4=50% to <70% affected, 5=70% to <90% affected, 6=90% to 100% affected). This degree score is used in the calculation of PASI score as shown in Table 5-1. The total percent body surface area (BSA) of PSO involvement will also be estimated as a number between 0 and 100.

Three aspects of the PSO lesion severity including erythema (redness), induration (thickness), and desquamation (scaling) are respectively rated on a 5-point scale (0=none, 1=slight, 2=moderate, 3=marked, and 4=very marked) across four body areas (head, upper limbs, trunk, and lower limbs). The sum of the three severity scale scores is weighted by the BSA involvement degree for each body area and aggregated into the PASI with prefixed weights (10% for head, 20% for upper limbs, 30% for trunk, and 40% for lower limbs). The PASI score ranges from 0 to 72 with a higher score indicating increased disease severity.

Details of calculations of PASI is provided in Section 6.1.6.1.

Table 5–1: Body areas for calculation of percent BSA for PASI

Table Body area	Details of area	BSA	Degree of involvement of body area ^a
Head	Face, back of head	10%	0 to 6
Upper extremities	Left, right, upper lower, flexor surface, extensor surface	20%	0 to 6
Trunk	Front, back, groin	30%	0 to 6
Lower extremities	Left, right, upper, lower, flexor surface, extensor surface, including buttocks	40%	0 to 6
Total		100%	

^a Where 0=none; 1=1% to <10% affected; 2=10% to <30% affected; 3=30% to <50% affected; 4=50% to <70% affected; 5=70% to <90% affected; 6=90% to 100% affected.

The PASI response is a binary variable based on the percent improvement from Baseline for each assessed timepoint. The percent improvement from Baseline for PASI for a participant will be calculated as:

$$\text{Percent Improvement from Baseline} = 100 \times \frac{\text{Baseline PASI} - \text{Post Baseline Timepoint PASI}}{\text{Baseline PASI}}$$

A participant will be classified as a PASI90 responder if his or her percent improvement at a timepoint is $\geq 90\%$. The PASI75, PASI50, and PASI100 response variables are defined in a similar fashion for PASI percent change from Baseline, ie, $\geq 75\%$, $\geq 50\%$, and $\geq 100\%$. The secondary PASI efficacy variables are PASI90 and PASI75 evaluated at Week 16 and Week 4:

- A PASI90 responder at Week 16 is a participant whose PASI percent improvement from Baseline is $\geq 90\%$ at Week 16.
- A PASI75 responder at Week 4 is a participant whose PASI percent improvement from Baseline is $\geq 75\%$ at Week 4.

5.4.1.1.2 IGA response

A static IGA will be used to assess PSO severity in all participants during the study. The IGA will be completed by the investigator on a 5-point scale as specified in [Table 5–2](#).

Table 5–2: Five-Point IGA

Score	Short Descriptor	Detailed Descriptor
0	Clear	No signs of psoriasis; post-inflammatory hyperpigmentation may be present
1	Almost clear	No thickening; normal to pink coloration; no to minimal focal scaling
2	Mild	Just detectable to mild thickening; pink to light red coloration; predominately fine scaling

Score	Short Descriptor	Detailed Descriptor
3	Moderate	Clearly distinguishable to moderate thickening; dull to bright red, clearly distinguishable to moderate thickening; moderate scaling
4	Severe	Severe thickening with hard edges; bright to deep dark red coloration; severe/coarse scaling covering almost all or all lesions

The IGA response is a binary variable based on the improvement from Baseline of the IGA score at each assessed timepoint. A participant will be classified as an IGA 0/1 responder for each assessed timepoint if his or her IGA response at a timepoint is clear (0) or almost clear (1) with at least a 2-category improvement from Baseline.

A participant will be classified as an IGA 0 responder for each assessed timepoint if his or her IGA response at a timepoint is clear (0) with at least a 2-category improvement from Baseline.

5.4.1.1.3 CDLQI (total score) change from baseline

The CDLQI (Lewis-Jones and Finlay, 1995) is a questionnaire designed to measure the impact of skin diseases on the lives of children. The questionnaire consists of 10 questions based on the experiences of children with skin disease concerning symptoms and feelings, leisure, school or holidays, personal relationships, sleep, and treatment. The questions relate to the impact of the skin disease on the child over the last week (ie, over the last 7 days) and are rated using a 4-point scale score from 0 to 3 (CCI [REDACTED]) (Table 5–3).

Participants will be asked to complete the CDLQI via an app. Any CDLQI data collected on paper via electronic data capture and digitally in the app will be pooled together for analysis. The CDLQI data source (ie, paper, app) will be displayed in the listing. All study participants, including those whose ages reach ≥ 17 years during the study, will complete the CDLQI throughout the study.

Table 5–3: Children’s Dermatology Life Quality Index (CDLQI) Scoring

CCI

[REDACTED]

The CDLQI total score is a continuous variable and calculated by summing the score of each question resulting in a maximum of 30 and a minimum of 0; the higher the score, the greater impairment on quality of life.

If 1 question is left unanswered, the unanswered question will be scored 0 and the scores are summed and expressed as usual out of a maximum of 30. If 2 or more questions are left

unanswered, the CDLQI total score will not be derived and will be missing. If responses are collected for both Q7A and Q7B, they will be displayed in the listing, however only the response corresponding to the answer given in Q7 will be tabulated.

5.4.1.2 Main analytical approach

5.4.1.2.1 PASI90 (Week 16) response

The estimand for the secondary efficacy endpoint PASI90 response at Week 16 is defined as follows:

- **Participant-level outcome:** PASI90 response at Week 16.
- **Treatment:** Bimekizumab high dose (Dose A) and low dose (Dose B).
- **Population:** Study participants enrolled according to the protocol-specified inclusion/exclusion criteria and randomized to IMP.
- **Intercurrent event handling:** An intercurrent event is defined as discontinuation of IMP prior to Week 16. A composite strategy will be implemented in which a positive clinical outcome is defined as achieving PASI90 response at Week 16 and not discontinuing IMP through Week 16.
- **Population-level summary:** Percentage of participants achieving PASI90 response at Week 16 in each dose group.

The number and percentages of PASI90 responders at Week 16 will be reported for each dose group with 95% CIs. Missing data not preceded by an intercurrent event will be imputed as nonresponse for this and other binary secondary efficacy variables. An OC method will also be implemented to assess the impact of the main method of handling missing data.

